4.2.5 Day of SRS

- 4.2.5.1** Documentation of corticosteroid use/no dexamethasone (or any other corticosteroid with the purpose of treating cerebral edema) use.

4.2.5.2 Continued fingerstick glucose draws by patient once a day (in the morning before breakfast [fasting]) for at least 1 week after SRS. Please see section 5.4.2 for further details.

4.2.6 1 week after SRS (± 3 days)

4.2.6.1 Review the patient's blood glucose and medication administration logs.

4.2.6.2 CBC with differential and CMP including LFTs.

4.2.6.3 Fingerstick Glucose draw by nurse/research team member.

4.2.6.4 Adverse event evaluation. If no "*concerning toxicity*" or "*serious toxicity*" (see section 5.3.2), then patient will be instructed to discontinue blood glucose monitoring.

4.2.6.4.1 If the patient does have a "*concerning toxicity*" or "*serious toxicity*" they must discontinue their investigational medication (see section 5.3.2) and thus can also discontinue with fingerstick glucose draws.

4.2.6.5 Documentation of corticosteroid use (record the date of initiation, dose and reason for initiation of any new corticosteroid, especially dexamethasone).

4.2.7 1 month after SRS (- 5 or + 10 days)

4.2.7.1 Discontinue investigational medication (last dose is taken the evening of obtaining the follow-up MRI). Have patient return all remaining (untaken) investigational medication tablets.

4.2.7.2 Follow-up brain MRI with and without contrast. T1-weighted, T2, and/or FLAIR MRI of the brain (maximum slice thickness 5mm). FLAIR imaging is preferred.

4.2.7.2.1 T1 post gadolinium sequence will be imported into the Eclipse treatment planning system and the radiation oncologist (who will be blinded to the patient's investigational medication) will contour the enhancing tumor that received the prescribed dose of SRS.

4.2.7.2.2 FLAIR sequence will be imported into the Eclipse treatment planning system. FLAIR volume will be automatically calculated using "Region Growing" on Eclipse (Appendix I). The automated contours will be verified and modified as needed by the radiation oncologist who will be blinded to the patient's investigational medication.

4.2.7.3 Follow-up history and physical with neurologic examination and corticosteroid use documentation (record the date of initiation, dose and reason for initiation of any new corticosteroid, especially dexamethasone). A last fingerstick glucose draw will be done by the nurse/research team member.

4.1.7.4 Review and collect the patient's blood glucose and medication administration logs.

4.2.7.5 Adverse event evaluation.

4.2.7.6 CBC with differential and CMP including LFTs.

4.2.8 3 months after SRS (- 10 or + 14 days)

4.2.8.1 Follow-up brain MRI with and without contrast. T1-weighted, T2, and/or FLAIR MRI of the brain (maximum slice thickness 5mm). FLAIR imaging is preferred.

4.2.8.1.1 T1 post gadolinium sequence will be imported into the Eclipse treatment planning system and the radiation oncologist (who will be blinded to the patient's investigational medication) will contour the enhancing tumor that received the prescribed dose of SRS.

4.2.8.1.2 FLAIR sequence will be imported into the Eclipse treatment planning system. FLAIR volume will be automatically calculated using "Region Growing" on Eclipse (Appendix I). The automated contours will be verified and modified as needed by the radiation oncologist who will be blinded to the patient's investigational medication.

4.2.8.2 Follow-up history and physical with neurologic examination and corticosteroid use documentation (record the date of initiation, dose and reason for initiation of any new corticosteroid, especially dexamethasone).

4.2.8.3 Adverse event evaluation.

4.2.8.4 CBC with differential and CMP including LFTs.

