4.1.5 Day of SRS

- 4.1.5.1** Documentation of corticosteroid use/no dexamethasone (or any other corticosteroid with the purpose of treating cerebral edema) use.
- 4.1.5.2** Continued fingerstick glucose draws by patient 4 times a day (in the morning before breakfast (fasting), before lunch, before dinner, and before bed) for at least 1 week after SRS.

4.1.6 1 week after SRS (\pm 3 days)

- 4.1.6.1** Review the patient's blood glucose and medication administration logs.
- 4.1.6.2** CBC with differential and CMP including LFTs.
- 4.1.6.3** Fingerstick Glucose draw by nurse/research team member.
- 4.1.6.4** Adverse event evaluation. If no "*concerning toxicity*" or "*serious toxicity*" (see section 5.3.1), then patient will be instructed to only obtain fingerstick glucose draws once a day (in the morning before breakfast [fasting]) until the day of discontinuation of glyburide.
 - 4.1.6.4.1** If the patient does have a "*concerning toxicity*" or "*serious toxicity*" they must discontinue glyburide (see section 5.3.1) and thus can also discontinue with their fingerstick glucose draws.
- 4.1.6.5** Documentation of corticosteroid usage (record the date of initiation, dose and reason for initiation of any new corticosteroid, especially dexamethasone).

4.1.7 1 month after SRS (- 5 or +10 days)

- 4.1.7.1** Discontinue glyburide (last dose is taken the evening of obtaining the follow-up MRI) and discontinue blood glucose monitoring. Have patient return all remaining (untaken) glyburide tablets.
- 4.1.7.2** Follow-up brain MRI with and without contrast. T1-weighted, T2 and/or FLAIR MRI of the brain (maximum slice thickness 5mm). FLAIR imaging is preferred.
 - 4.1.7.2.1** T1 post gadolinium sequence will be imported into the Eclipse treatment planning system and the radiation oncologist will contour the enhancing tumor that received the prescribed dose of SRS.
 - 4.1.7.2.2** FLAIR sequence will be imported into the Eclipse treatment planning system. FLAIR volume will be automatically calculated using "Region

“Growing” on Eclipse (Appendix I). The automated contours will be verified and modified as needed by the radiation oncologist.

- 4.1.7.3** Follow-up history and physical with neurologic examination and corticosteroid use documentation (record the date of initiation, dose and reason for initiation of any new corticosteroid, especially dexamethasone). A last fingerstick glucose draw will be done by the nurse/research team member at this visit.

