4.2.3 Within 21 days prior to SRS

- 4.2.3.1** Follow-up brain MRI with and without contrast. T1-weighted, T2, and/or FLAIR MRI of the brain (maximum slice thickness 5mm). FLAIR imaging is preferred.
 - 4.2.3.1.1** T1 post gadolinium sequence will be imported into the Eclipse treatment planning system and the radiation oncologist (who will be blinded to the patient's investigational medication) will contour the enhancing tumor that received the prescribed dose of SRS.
 - 4.2.3.1.2** FLAIR sequence will be imported into the Eclipse treatment planning system. FLAIR volume will be automatically calculated using "Region Growing" on Eclipse (Appendix I). The automated contours will be verified and modified as needed by the radiation oncologist who will be blinded to the patient's investigational medication.

4.2.4 5-9 days prior to SRS

- 4.2.4.1** Randomization will occur (can be any time after registration/study entry and up until 5-9 days prior to SRS).
- 4.2.4.2** Documentation of corticosteroid use/no dexamethasone (or any other corticosteroid with the purpose of treating cerebral edema) use.
- 4.2.4.3** Give patient a sufficient supply of investigational medication: either non-micronized Glyburide tablets (1.25 mg) or placebo, to be taken orally twice a day (in the morning with breakfast and in the evening with dinner). Missed doses will not be made up. Patient, physicians, and the study team will be blinded to the investigational medication. Patient should be instructed to begin investigational medication at least 5 days prior to SRS and continue investigational medication until the evening dose of the one month post SRS MRI scan.
- 4.2.4.4** Provide patient with study supplies that include a medication/blood glucose log (for recording time of taking the investigational medication as well as time and value of blood glucose draws), a blood glucose monitor, and handouts for education purposes. The patient will be educated on how to measure and record blood glucose values (see Appendices II-VI).
- 4.2.4.5** Patient should begin fingerstick glucose draws once a day beginning the day of investigational medication initiation (in the morning before breakfast [fasting]). Please see section 5.4.2 for further details. An additional fingerstick glucose draw will be taken by the nurse/research team member at this visit.

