5.4 Safety and efficacy (blood glucose monitoring)

5.4.1 Pilot Portion

All patients will be provided with a medication/blood glucose log, a blood glucose monitor, and taught to perform self fingerstick glucose draws (see Appendices II-VI). The first blood glucose draw will be done by a nurse or research team member on the visit 5-9 days prior to SRS and the initial value will be recorded in the blood glucose log. Starting at the initiation of glyburide and for at least the first week after SRS, the patient will take and record blood glucose levels 4 times a day (in the morning before breakfast [fasting], before lunch, before dinner, and before bed). After one week post SRS, if the patient does not experience a dose limiting toxicity (DLT, as defined in section 5.3.1), he/she will be instructed to obtain blood glucose levels once a day (in the morning before breakfast [fasting]) until the discontinuation of glyburide. If the patient does experience a DLT then he/she must discontinue glyburide (as per section 5.3.1) and will not have to continue checking their blood glucose levels.

If the patient is symptomatic and this is thought to be attributable to hypoglycemia, he/she should check a fingerstick glucose level and begin “low blood sugar intervention” as described in **Section 5.4.1.1** (also see Appendix IV). If fingerstick glucose levels reach ≤ 80 mg/dl (symptomatic or asymptomatic), the patient should begin “low blood sugar intervention”. If “low blood sugar intervention” does not cause the blood sugar to rise above 80 mg/dl, or if symptoms persist, the patient will be instructed to contact the study team and/or call 911 for emergency services.

5.4.1.1 “Low Blood Sugar Intervention”:

Procedures:

1. Take 15 grams of carbohydrate:
 - a. 3 or 4 glucose tablets or
 - b. 4 oz (1/2 cup) of fruit juice or
 - c. 6 oz regular soda (about 1/2 can)
2. Rest and wait 15 minutes
3. Recheck blood sugar

4. Repeat Steps 1-3 if blood sugar still less than 80 mg/dl
5. If next meal is more than 1 hour away, eat a snack.

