5.4.2 Randomized Portion

5.4.2.1 All patients will be provided with a medication/blood glucose log, a blood glucose monitor, and taught to perform self fingerstick glucose draws (see Appendices II-VI). The first blood glucose draw will be done by a nurse or research team member on the visit 5-9 days prior to SRS and the initial value will be recorded in the blood glucose log.

5.4.2.2 If the Pilot Portion (at either full dose or at one dose reduction) demonstrates no "**serious toxicities**" and ≤ 3 "**concerning toxicities**" (described in section 5.3.1), patients in the Randomized Portion of the trial will be taught and instructed to measure blood glucose levels once a day (in the morning before breakfast (fasting)) starting at the initiation of the investigational medication and continuing for at least the first week after SRS. If no "**concerning toxicities**" or "**serious toxicities**" are found at the one week post SRS visit, then the patient may proceed through the rest of the trial with no further need to assess blood glucose via the fingerstick draws. If the patient does experience a "**concerning toxicity**" or "**serious toxicity**" then he/she must discontinue their investigational medication (as per section 5.3.2) and will not have to continue checking their blood glucose levels.

5.4.2.3 If the Pilot Portion (at either full dose or at one dose reduction) demonstrates no "**serious toxicities**" and 4-5 "**concerning toxicities**" (described in section 5.3.1), patients in the Randomized Portion of the trial will be taught and instructed to measure blood glucose as per section 5.4.1.

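### The randomized week-1 instruction (4.2.6.4) stops glucose self-monitoring unconditionally, which contradicts 5.4.2.3 if the pilot shows 4-5 concerning toxicities

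*Combined protocol and SAP*

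**What the plan says.** Section 5.4.2 gives the Randomized Portion two glucose-monitoring rules and lets the pilot result choose between them.

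- **5.4.2.2** (no serious, at most 3 concerning toxicities): one fasting check a day to at least one week after SRS. If week 1 is clear, "then the patient may proceed through the rest of the trial with no further need to assess blood glucose via the fingerstick draws".
- **5.4.2.3** (no serious, 4-5 concerning toxicities): "patients in the Randomized Portion of the trial will be taught and instructed to measure blood glucose as per section 5.4.1".

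Section 5.4.1 is the pilot regimen. From drug start to at least one week after SRS, "the patient will take and record blood glucose levels 4 times a day". After that, a patient without a dose-limiting toxicity steps down: "he/she will be instructed to obtain blood glucose levels once a day (in the morning before breakfast [fasting]) until the discontinuation of glyburide".

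The visit-by-visit text for the Randomized Portion reads as follows.

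- **4.2.4.5**, drug start: "Patient should begin fingerstick glucose draws once a day beginning the day of investigational medication initiation". It refers to 5.4.2.
- **4.2.5.2**, day of SRS: "Continued fingerstick glucose draws by patient once a day (in the morning before breakfast [fasting]) for at least 1 week after SRS". It also refers to 5.4.2.
- **4.2.6.4**, week 1: with no concerning or serious toxicity, "then patient will be instructed to discontinue blood glucose monitoring". It refers only to 5.3.2, which defines the toxicities and does not set a monitoring frequency.

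The pilot counterpart, 4.1.6.4, does contain the step-down. At the same visit a toxicity-free pilot patient is told to "only obtain fingerstick glucose draws once a day (in the morning before breakfast [fasting]) until the day of discontinuation of glyburide".

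**The concern.** Under 5.4.2.2 the visit instruction and the rule agree. Under 5.4.2.3 they do not: one tells staff to end self-monitoring at week 1, the other requires daily checks until the investigational medication stops at the one-month MRI. Staff cannot do both, and 4.2.6.4 is the text they would have open when instructing the patient.

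Asymptomatic grade 3 or 4 hypoglycemia counts as a concerning toxicity under 5.3.2 and requires stopping the drug. Without symptoms it is found only by measuring glucose. The branch in question is also the one where 4 or 5 of 10 pilot patients have already had a concerning toxicity, which is presumably why 5.4.2.3 keeps the heavier monitoring. Following 4.2.6.4 would remove that safeguard while dosing continues.

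**Working it through.** **1. Can the branch occur?** The pilot triggers a dose reduction (or termination, at the reduced dose) only at 6 or more concerning toxicities or at least 1 serious toxicity among 10 evaluable patients (5.3.1, 9.3.1). A result of 4-5 concerning and no serious therefore proceeds to randomization. The plan's own figures in 9.5.1 reproduce under this rule:

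- P(at most 5 of 10 concerning | 30%) = 0.953 (stated 95%)
- P(at least 6 of 10 concerning | 70%) = 0.850 (stated 85%)
- P(no serious in 10 | 1%) = 0.99^10 = 0.904 (stated 90%)
- P(at least 1 serious in 10 | 30%) = 1 - 0.7^10 = 0.972 (stated 97%)

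**2. How likely is it?** Treat each of 10 independent patients as concerning (probability c), serious (s) or neither. For one cohort,

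B = C(10,4) c^4 (1-c-s)^6 + C(10,5) c^5 (1-c-s)^5.

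At c = 0.30 and s = 0.01: 210 × 0.30^4 × 0.69^6 + 252 × 0.30^5 × 0.69^5 = 0.184 + 0.096 = 0.279.

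A dose reduction after the first cohort has probability R = 1 - Σ(k=0..5) C(10,k) c^k (1-c-s)^(10-k). A second cohort at the same rates gives B + R × B. If the reduced dose halves both rates, the second B is computed at c/2 and s/2.

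| c (s = 0.01) | B, one cohort | R | Two cohorts, same rates | Two cohorts, rates halved |
|---|---|---|---|---|
| 0.30 | 0.279 | 0.140 | 0.319 | 0.286 |
| 0.20 | 0.106 | 0.102 | 0.117 | 0.108 |
| 0.10 | 0.012 | 0.096 | 0.013 | 0.012 |
| 0.05 | 0.001 | 0.096 | 0.001 | 0.001 |

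The 30% is the tolerable operating point in 9.5.1.2. The 1% is the rate used in 9.5.1.1, which appears under serious toxicities but is worded there as grade 3 hypoglycemia. The 20%, 10% and 5% rates and the reduced-dose rates are assumptions.

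**3. What is lost after week 1?** The week-1 visit is day 7 ± 3, and the one-month visit, when the drug stops, is day 30 (-5/+10).

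- Nominal: 30 - 7 = 23 days
- Shortest: 25 - 10 = 15 days
- Longest: 40 - 7 = 33 days (day 7 rather than day 4, because 4.2.5.2 keeps checks going for at least one week)

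At one check a day, that is the number of required checks lost per patient. Staff fingersticks and metabolic panels are scheduled at the week-1 and one-month visits, with no glucose measurement between them.

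**4. Is there a gap before week 1?** Taken alone, the once-daily wording in 4.2.4.5, 4.2.5.2 and Appendix VIII footnote 3 falls 3 checks a day short of 5.4.1. Drug starts 5-9 days before SRS. To day 7 the shortfall is 3 × (5+7) = 36 to 3 × (9+7) = 48 checks. With a day-10 visit it is 3 × (5+10) = 45 to 3 × (9+10) = 57. The overall range is 36-57, but this arises only if the cross-references to 5.4.2 are ignored.

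**The case against.** The best defense is that the design in 5.4.2 is clear and the visit schedule is only shorthand for it. Several parts of this stand.

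- A reader might infer that the whole randomized schedule implements only 5.4.2.2. The documents do not support that. 4.2.4.5, 4.2.5.2 and footnote 3 all send the reader to 5.4.2, and the patient sheet in Appendix II defaults to four checks a day unless the study team relaxes it. The once-daily wording is therefore a lesser inconsistency.
- Footnote 4 of the randomized schedule might be read as a second contradiction. It says when self-checks may stop and does not order a stop, so it is incomplete rather than contradictory. It has no pointer to 5.4.2, and the one-month column has no patient fingerstick entry, although the pilot table has one.
- Patients would not be left without any means of detection. They have a meter, and Appendix II tells them to check when they feel symptoms. The loss is in routine detection of asymptomatic events.
- The Data Safety Monitoring/Quality Assurance Committee must review and approve the pilot data before randomization starts (5.2), so the applicable branch will be known in advance. That lowers the practical risk, but nothing in 5.2 changes what 4.2.6.4 tells staff to do.
- The branch may be unlikely. A concerning toxicity through asymptomatic hypoglycemia means glucose below 40 mg/dL (Appendix VII), and the documents give no expected rate at this dose. Under 7.1.4, a dose-limiting toxicity before SRS makes a pilot patient inevaluable, so early events would not count toward 4-5 of 10.

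None of this reconciles the week-1 instruction with 5.4.2.3.

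**Conclusion.** The contradiction between 4.2.6.4 and 5.4.2.3 is real, conditional on the pilot result, and should be corrected. It exists only if the pilot cohort that leads to randomization shows no serious and 4-5 concerning toxicities; under 5.4.2.2 the texts agree. Within the branch, following 4.2.6.4 would cost each toxicity-free patient about 23 days (15-33) of required daily checks. The only inputs to that figure are the protocol's visit windows.

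The probability of the branch is much less certain. It runs from about 28% at a 30% concerning rate to 0.1% at 5% for one cohort. It assumes independent patients and a 1% serious rate, and a second cohort changes it little. A reader might take 28% as the expected chance, but 30% is a tolerability operating point, not a forecast.

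Nor does the point bear on the efficacy analysis: sample size, power and the type I error rate are unaffected. It concerns internal consistency in safety monitoring.

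**What to change.** - **4.2.6.4:** make the week-1 stop apply only under 5.4.2.2. State that under 5.4.2.3 a toxicity-free patient steps down to one fasting check a day until the investigational medication stops, adapting the wording of 4.1.6.4.
- **Appendix VIII, Randomized Portion:** add a reference to 5.4.2 in footnote 4, and a patient fingerstick entry in the one-month column marked as applying under 5.4.2.3.
- **4.2.4.5, 4.2.5.2 and footnote 3 (lower priority):** state once a day under 5.4.2.2 and four times a day under 5.4.2.3, so that the frequency does not depend on following the cross-reference.

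The cost is an amendment of wording. No new procedure is added, because 5.4.2.3 already requires these checks, and no change to sample size or analysis follows.

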4.2.9 Conditions for early patient stopping of investigational medication

4.2.9.1 A dose limiting toxicity (DLT) is reached. See section 5.3.2.

4.2.9.2 Patient requires corticosteroid administration after registration but prior to SRS, please note these patients will be deemed inevaluable.

5.0 STUDY DESIGN AND TREATMENT SUMMARY

Please see the Treatment Schema on pages 3-4 for detailed diagrams. Due to COVID-19, these study procedures may be conducted remotely, if necessary.

5.1 Pilot Portion

10 evaluable patients will be enrolled onto the Pilot Portion. Should there be a glyburide dose reduction, 10 evaluable patients at this lower glyburide dose must be assessed. Inevaluable patients will be replaced.

Patients with brain metastases, who are not taking dexamethasone (or any other corticosteroid with the purpose of treating cerebral edema) within 5 days prior to SRS, after informed consent, will be treated with:

1. Non-Micronized glyburide (1.25 mg orally twice a day (po BID)) should begin 5 days prior to SRS to be taken until the evening dose on the day of the one month follow-up MRI.
2. Radiosurgery will be linac-based and must be initiated at least 5 days after starting glyburide (can be more for patients being treated with linac-based radiosurgery where the MRI may be done within 21 days prior to SRS treatment).

For treatment planning and at the time of the one and three month follow-up appointments, the patient must undergo a brain MRI with and without contrast. T1-weighted, T2, and/or FLAIR MRI of the brain (maximum slice thickness 5mm). FLAIR imaging is preferred. The treatment planning MRI may be done within 21 days prior to SRS treatment only for patients being treated with linac-based radiosurgery where it is not standard of care to complete a MRI on the day of SRS (as it is with gamma knife).

T1 post-gadolinium sequences and FLAIR axial sequences from the treatment planning MRI (see note above regarding linac-based radiosurgery patients) and at the one and three month follow-up appointments will be imported into the Eclipse treatment planning system. On the T1 post gadolinium sequences, the radiation oncologist will contour the enhancing tumor that received the prescribed dose of SRS. Using the FLAIR sequences Eclipse will automatically calculate FLAIR volume using “Region Growing” (Appendix I). The automated contours will be verified and modified as needed by the radiation oncologist.

5.1.1 Patients can only be enrolled after all eligibility criteria are met. The date of registration/enrollment/study entry is considered to be the day the Eligibility Checklist is signed by the verifying physician and should be no later than 5-9 days prior to SRS. Once a patient is enrolled, a unique case number will be assigned.

